5.1 Inclusion Criteria

Candidates must meet the first inclusion criteria and either one of the last two criteria in order to participate in the study.

- Ages 18 and older
- Healthy volunteers
- AMD, diabetic retinopathy, central serous chorioretinopathy, and/or glaucoma or glaucoma suspects or any other suspected eye disease
- Face length of less than or equal to 6.900 inches

Version: 3.0

Group-Specific Inclusion Criteria

There are no group-specific inclusion criteria for subjects with AMD, diabetic retinopathy, and central serous chorioretinopathy.

Healthy

A normal clinical ophthalmic examination.

Primary Open Angle Glaucoma (POAG)

- Clinical characteristics of glaucoma: optic nerve head (ONH) abnormalities: global rim thinning, rim notch, or disc hemorrhage; retinal nerve fiber layer (RNFL) defect.
- Typical glaucomatous field loss in reliable VF, reproducible glaucoma hemifield tests labeled outside normal limits on at least two consecutive tests.
- Good quality (adequate signal strength ≥ 6/10, without segmentation algorithm failure and motion artifacts > 1 vessel diameter) RNFL and GCIPL OCT, labeled outside normal limits with typical glaucomatous RNFL and GCIL thinning.

Normal Tension Glaucoma (NTG)

Identical to POAG criteria with IOP recorded at ≤ 21 mmHg at any time point.

5.2 Exclusion Criteria

An individual who meets any of the following criteria will be excluded from participation in this study:

- 1. Any medical treatment (e.g., chronic corticosteroid, hydroxychloroquine, chloroquine, thioridazine, canthaxanthine) or conditions that affect VF (e.g., stroke) and retinal thickness other than glaucoma.
- 2. Face length of over 6.900 inches

5.3 Strategies for Recruitment and Retention

Healthy volunteers, and patients with glaucoma, AMD, DR, and/or CSCR as well as any other eye disease will be enrolled consecutively from NYU Department of Ophthalmology from the investigators and the research team's clinics, recruitment telephone script and via IRB-approved messaging through the MyChart portal in Epic. The study does not require a screening procedure, and all qualified subjects will be offered to participate in the study. Potential candidates will be informed by their clinician or a clinical coordinator from the research team. The participants will receive a comprehensive explanation about the study, risks and benefits and will be encouraged to ask questions related to the study. We will emphasize that participation is voluntary. Documentation of the informed consent process will be used to ensure that the appropriate questions have been asked to the perspective participant. Only study personnel will conduct consenting process. For candidates who are not fluent in English, NYU translation services will be used to ensure that the candidate fully understands the study and the consent. We anticipate on encountering subjects that are fluent in a language other than English. Therefore, the informed consent will be translated in the following languages following initial approval: Spanish and Korean, For an unexpected enrollment (subject doesn't speak English, Spanish, Korean but meets all inclusion criteria), we will use the short form with an interpreter and then will have the ICF translated in the subject's language and submitted via modification to the IRB to allow for any reconsenting in the future if necessary as well as to enroll other subjects who speak this particular language.

Participation in the study and data collection will be possible only after subjects have signed consent.

5.3.1 Use of DataCore/Epic Information for Recruitment Purposes

Version: 3.0

This study will utilize EPIC to identify subjects. Data and records will be sourced for EPIC. Data will be gathered upon request by DataCore and be used for case identification as well as collecting information. The data team will search EPIC weekly. Medical records will be screened by initially filtering for all patients that are diagnosed as healthy, primary open angel glaucoma, and normal tension glaucoma from 2022-2026. Identified patients will then have their electronic medical records reviewed based on the protocol's outlined inclusion and exclusion criteria. Protected health information that will be used during this study includes patient name, zip code, date of birth, and specific date of birth for patients over 90 years in stead of recording their as "90 or older". Patient names will temporarily be used while determining eligibility but will not be used for data analysis. Date of birth and specific date of birth for patients over 90 years instead of recording their age as "90 or older" will be used to determine eligibility and to group patients by age during data analysis. Data will be collected and recorded using Microsoft Excel. Data will be stored within an NYULH MCIT-managed network shared drive and be subsequently deleted from the shared drive upon completion of the study. Data will be accessible to the principal investigator, sub-investigator, coordinators and study team members.

Data Points and PHI used in EPIC search:

- Age
- Name
- Date of birth
- Diagnosis (Healthy, Primary Open Angel Glaucoma, Normal tension glaucoma, AMD, diabetic retinopathy, central serous chorioretinopathy, and/or glaucoma or glaucoma suspects or any other suspected eye disease)

To minimize risks to subjects and/or potential breach of confidentiality, only information required to answer the previously listed research objectives will be acquired. Additionally, any potential disclosure outside of research would not put subjects at risk or harm.

Any recruitment information sent by email will utilize Send Safe email.

Once potential subjects have been identified, the study team will notify the treating physician (TP) by email that they have patients eligible to participate as one of the following:

- Provide TP with a list, advertisement, letters or oral script to use when contacting potential subjects
- TP and Research PI send letter to all potential subjects (letter must have both TP and Research PI's name)
- TP agrees to permit study team to directly contact potential subjects on behalf of TP.
- TP has been notified that the study team will contact potential subjects directly, by letter, phone, email, or the MyChart portal etc.

The patients will be contacted either by MyChart, in-person during their clinic visit at the eye center or prior to their visit using a phone script (attached).

Once contact is made, approved recruitment language will be used to communicate the reason they are being contacted and subjects will be asked if they are interested in participating in this specific study. Should the potential subjects agree, the study team will provide the subjects with information regarding the next steps for participation.

If a subject requests information regarding opting out of further recruitment for all research, subjects will be directed to contact [contact] or [name].

5.4 Data Storage and Confidentiality

Data collection is the responsibility of the study staff at the site under the supervison of the site PI. The investigator is responsible for ensuring the accuracy, completeness, legibility, and timeliness of the data reported. Confidentiality will be held in strict trust by the research team. Medical record review will be limited

Version: 3.0

to just the elements needed to complete the study. Information about individual subjects will not be shared with anyone outside of the study team.

Study data will be stored in Trialmaster used in the NYU Langone Health Department of Ophthalmology. Subject data will be stored until the completion of data analysis and will subsequently be removed from the shared drive upon completion.

5.5 Duration of Study Participation

Besides for the screening, which is discussed in the previous section, the duration of study participation is solely for the one-time imaging session, i.e. one day. There is also no follow-up period.

5.6 Total Number of Participants and Sites

Recruitment will end when approximately 150 participants are enrolled at NYUMC.

5.7 Participant Withdrawal or Termination

5.7.1 Reasons for Withdrawal or Termination

Participants are free to withdraw from participation in the study at any time upon request. An investigator may terminate participation in the study if:

- Any clinical adverse event (AE), laboratory abnormality, or other medical condition or situation
 occurs such that continued participation in the study would not be in the best interest of the
 participant
- The participant meets an exclusion criterion (either newly developed or not previously recognized) that precludes further study participation
- Subjects may withdraw, at any time, their consent for participation in this research study.
 Subjects who are unduly distressed and cannot complete the research requirements will be withdrawn from the study. Any identifiable research or medical information recorded for, or resulting from, subject participation in this research study prior to the date that subject formally withdrew consent may continue to be used and disclosed by the investigators for the purposes described above.

5.8 Premature Termination or Suspension of Study

This study may be temporarily suspended or prematurely terminated if there is sufficient reasonable cause. Written notification, documenting the reason for study suspension or termination, will be provided by the suspending or terminating party to the Principal Investigator. If the study is prematurely terminated or suspended, the PI will promptly inform the IRB and will provide the reason(s) for the termination or suspension.

Circumstances that may warrant termination or suspension include, but are not limited to:

- Determination of unexpected, significant, or unacceptable risk to participants
- Demonstration of efficacy that would warrant stopping
- Insufficient compliance to protocol requirements
- Data that are not sufficiently complete and/or evaluable
- Determination of futility

Study may resume once concerns about safety, protocol compliance, data quality are addressed and satisfy the IRB and/or FDA.

Version: 3.0

6 Study Agent (Study drug, device, biologic, vaccine etc.) and/or Procedural Intervention

6.1 Study Device Description

The device, chin and forehead rest, has its provisional patent currently filed to the USPTO.

Its constituent parts may include, but are not limited to other possible configurations as listed in the patent, and are described and can be seen in further details in the tables below.

Table 1 shown below provides the Bill of Materials for the Chin rest. It includes the material used, quantity along with a description of the component.

| Part | Qty. | Description | Material |
|----------------------|------|------------------------------|------------------------|
| | | | |
| Chin rest Base Front | 1 | patient rests chin on | ABS/ Biomed Back Resin |
| Chin rest Base Back | 1 | 2 threaded holes for knobs | Steel |
| Rotary Shaft | 2 | extension mechanism | 316 Stainless Steel |
| Bearing | 4 | reduces friction along shaft | 841 Bronze |
| Head Thumb Screw | 2 | locking mechanism | Steel low profile |

Table 1: Chin Rest - Bill of Materials

In Table 2 below, the bill of materials is provided for the mount and attachment for the chin rest.

| Part | Qty. | Description | Material |
|---------------------|------|---|-----------------|
| Clamp (male) | 1 | half of clamp (specific to each device) | ABS |
| Clamp (female) | 1 | half of clamp (specific to each device) | ABS |
| Lock - Threaded Rod | 1 | locking mechanism for attachment to device | Stainless Steel |
| Slide Lock | 1 | locking mechanism for extending the mount | Stainless Steel |
| Threaded Pin | 1 | connects male and female clamp | Stainless Steel |
| Edge Adjuster | 4 | adjusts mount size according to chin rest extension | ABS |

Table 2: Mount & Attachment - Bill of Materials

A further description of the device and its potential configurations can be found in section 2.2 as well as the provisional patent application attached.

The device is not a significant risk device as it is solely being used to stabilize the subject's head. The materials in contact with the patient are biocompatible and will also be sterilized and sanitized accordingly. The device does not meet the 4 criteria for Significant Risk device in accordance with 21CRF 812.3(m), because (1) it is not intended as an implant (2) It is not purported or represented to be for a use in supporting or sustaining human life (3) It is not for a use of substantial importance in diagnosing, curing, mitigating, or treating disease, or otherwise preventing impairment of human health; (4) Does not

Version: 3.0

Otherwise presents a potential for serious risk to the health, safety, or welfare of a subject. The results of the imaging using the investigational device will not be used to make a clinical diagnosis or guide care.

6.1.1 Acquisition

Silicone components of the device will be supplied by the manufacturer, Zetar and will be shipped directly to the Principal Investigator in the NYU Ophthalmology Clinic. Any components that are made from some form of metal will be purchased and sourced directly from the mainstream hardware suppliers, such as McMaster Carr. The remainder of parts will be produced and acquired by the hospital makerspace or machine shop.

6.1.2 Formulation, Appearance, Packaging, and Labeling

The device is comprised of various components. Depending on the complexity and availability for these components to be sourced off the shelf the remainder will either be manufactured in house by the mechanical engineers and machinists in NYU and the silicone related parts will be manufactured by Zetar, a Silicone manufacturing factory in China. All components will be sourced with the constraint of each material being biocompatible as to not cause any irritation to the subjects when they are resting their head on the chin and forehead rest.

6.1.3 Product Storage and Stability

The device storage requirements include:

- -20 to 80 degrees Celsius, as outside that range the ABS parts mechanical properties vary with temperature
- 2. Avoid being in areas containing a high humidity as that can increase the rate of corrosion of the stainless steel components
- 3. Secured in a container as to avoid contamination of the components

6.1.4 Preparation

Preparation of the device includes solely the mounting of the device to the existing OCT Imaging devices one time before a day of imaging subjects by the study staff.

The instructions are as follows:

- 1. Remove the device from the container and calibrate the device by measuring the length of the subject's face.
- 2. Attach the chinrest mount to the OCT Imaging devices by placing the top and bottom parts of the invention, shown in the provisional patent attached, to the existing chinrest of the imaging device
- 3. Click into place the right and left pieces into the extruded holes in the top and bottom parts of the attachment, shown in the second configuration of the chinrest mount in the provisional patent
- 4. Push the ball joint section of the plate into one of the two grooved holes on the top of the attachment, either the right or left one depending on whether the OD/OS will be imaged first
- 5. Wipe the exposed parts of the chinrest with an alcohol swab
- 6. Secure the forehead rest attachment to the existing Cirrus device by sliding the clip down the front of the existing forehead rest
- 7. Wipe the exposed parts of the forehead rest with an alcohol swab

6.1.5 Administration

The order in which a subject will be imaged on either OCT imaging device C/N and whether the Imager will begin with either the OD/OS eye will be randomized. This will be done by providing the NYU Ophthalmology Clinic with a total of 90 envelopes that the Imager will choose from a mixed pile in which they will be evenly divided with a message to begin with device C/N and to begin with eye OD/OS.

The Standard Operating Procedure as to how to operate the novel device for imaging a subject can be seen below:

Version: 3.0

- 1. Sanitize chin and forehead rest
- 2. Seat subject by device
- 3. Move chinrest to either OD/OS
 - a. Slide chinrest to either right/left side
- 4. Size chinrest
 - a. Subject should place their chin in the rest and technician should either pull apart/push together the chin rest to either make it larger/smaller to fit the patient
- 5. Size mount of chinrest
 - a. Pull apart the mount easily to allow for the chinrest's length to be extended
- 6. Lock extension
 - a. Rotate knobs on both sides
- 7. Find correct/comfortable angular position of the chinrest
 - a. Push/move chinrest to position that it is comfortable i.e. not protruding into subject's neck and subject feels relaxed
- 8. Lock rotation
 - a. Tighten the bolt placed around the ball joint
- 9. Subject should rest forehead against the rest
- 10. Technician /imager should check if subject has to be adjusted closer to the device (based on the image from the device)
 - a. push/pull forehead rest by side of device so it will be adjusted along the grooved slot
- 11. Size forehead rest
 - a. tighten/loosen the strap on the side of the forehead rest to either make it smaller/larger for the patient (it will automatically lock into place)
- 12. Check if subject is comfortable, adjust if need be
- 13. Image subject according to scan protocol

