| Title | Comfortable and Stabilizing Chin & Forehead Rest Attachment for Slit Lamp Configurations |
|---|---|
| Short Title | Invention Study |
| Brief Summary | Cohort will consist of 150 subjects consisting of those that are healthy or have an existing eye disease. Subjects will be imaged on two OCT devices: device N, invention attached to the device and device C, the standard conventional device. The Imager will time multiple durations, one of them which will act to evaluate the number of motion artifacts that arise due to both the instability and lack of comfort the patient is experiencing in that particular moment. Following the imaging session, subject will be asked which device was more comfortable. |
| Phase | NA |
| Objectives | The primary objective is to ascertain that the OCT Imaging device with the invention attached provides a more comfortable experience for the subject. While the secondary objective is to reduce the time it takes for the system to account for the number of motion artifacts. |
| Methodology | Randomized |
| Study Duration | Until target number of subjects is reached |
| Participant Duration | One clinic visit |
| Duration of IP administration | One clinic visit |
| Study Sites | NYU Department of Ophthalmology |
| Number of participants | 150 subjects |
| Description of Study Agent/Procedure | Comfortable chin and forehead rest that can be adjusted to fit each individual's size. |
| Statistical Analysis | Descriptive statistics for continuous variables and categorical data, presented using frequency counts and percentages will be used for group and device comparison. Patient experience will be assessed using two-sided exact test of proportion. Comfort levels of each device will be compared using t test. Linear mixed effect models will be utilized to compare the time duration while accounting for inter-eyes correlations. |

Version: 3.0

Schematic of Study Design

Screening Period

- Total n=150
- · Obtain informed consent
- Screen potential subjects by inclusion and exclusion criteria
- Obtain history, document

Day of Imaging

1. Randomize Order of Devices

 Provide clinic with 150 envelopes in which they are assigned with instructions regarding which device and eye the Imager should begin with (C/N & OS/OD)

2. Study Intervention

- Measure the length of the subject's face
- Provide subject with questionnaire containing the following
 - o Are you feeling well?
 - o Are you feeling tired today?
 - o Are you uncomfortable?

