2.3 Rationale

This study primarily focuses on increasing the comfort for each patient's experience as well as reducing motion artifacts by improving the former, as well as stabilizing the patient's head, accomplished by adjusting the chin and forehead rest for each individual patient. The cohort will consist of a total of 90 subjects consisting of subjects that are both healthy and have an existing eye disease, as commonly observed in ophthalmology outpatient offices.

In order for certain limitations to not affect the validity of the results, various aspects of the trial will be randomized. This includes, but is not limited to, the order in which a patient will begin being imaged on either device C/N and which eye, OS/OD the Imager will scan first. This can help account for parameters including whether the time it takes to image the patient and/or level of comfort is affected as a result of their degree of alertness, energy level, how they are feeling on that particular day, etc.

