14.3 Participant Reimbursements or Payments

All participating subjects will receive \$20 as compensation for their time.

15 Interest Policy

The PI, [name], has potential conflicts of interest with this project. NYU COI committee have established a management plan that will be implemented for this project.

Version: 3.0

16 References

2. CDC. Don't Let Glaucoma Steal Your Sight! Centers for Disease Control and Prevention. Published November 24, 2020. https://www.cdc.gov/visionhealth/resources/features/glaucoma-awareness.html

3. Orbis International. Global blindness was slowing prior to pandemic study reveals. Orbis. Published October 11, 2021. https://www.orbis.org/en/news/2021/new-global-blindness-data

Version: 3.0

17 Attachments

These documents are relevant to the protocol, but they are not considered part of the protocol. They are stored and modified separately. As such, modifications to these documents do not require protocol amendments.

- 1. New Research Project Feasibility Questionnaire
- 2. Questionnaire for Subjects
- 3. Provisional Patent for the Novel Device
- 4. Recruitment telephone script

Study number: s22-01420 Version: 3.0

18 Schedule of Events

| Study team procedures X Consent subject X Select randomized imaging protocol X Clean first imaging device and attachments X Adjust chin rest / head mount X First imaging session survey X Clean second imaging device and attachments X Adjust chin rest / head mount X Image subject X Second imaging session survey X | Activity | Study Visit |
|--|---|----------------|
| ants | Study team procedures | |
| ants | Consent subject | × |
| stu | Select randomized imaging protocol | × |
| nd attachments | Clean first imaging device and attachments | × |
| nd attachments | Adjust chin rest / head mount | × |
| nd attachments | Image subject | × |
| Clean second imaging device and attachments X Adjust chin rest / head mount X Image subject X Second imaging session survey X | First imaging session survey | × |
| Adjust chin rest / head mount X Image subject X Second imaging session survey X | Clean second imaging device and attachments | × |
| Image subject X Second imaging session survey X | Adjust chin rest / head mount | × |
| Second imaging session survey | Image subject | × |
| | Second imaging session survey | × |

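### The Imager, who fits the device and times the scan, picks each order envelope from an unnumbered pile, and the pile may be 60 envelopes short of enrolment

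*Combined protocol and SAP*

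**What the plan says.** Every subject is imaged on both devices (section 4.1), so what is randomised is order. Section 2.3 says the randomised elements include "the order in which a patient will begin being imaged on either device C/N and which eye, OS/OD the Imager will scan first", and gives alertness, energy level and how the subject feels that day as the reason.

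The method is in section 6.1.5. The clinic receives "a total of 90 envelopes", and "the Imager will choose from a mixed pile in which they will be evenly divided". The Schematic of Study Design gives a different number: "Provide clinic with 150 envelopes in which they are assigned with instructions regarding which device and eye the Imager should begin with". Section 5.6 states "Recruitment will end when approximately 150 participants are enrolled at NYUMC", while section 2.3 states "The cohort will consist of a total of 90 subjects", and section 10.2 also works with 90.

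The schedule in section 18 lists only "Select randomized imaging protocol", after consent. No section says that the envelopes are sealed, opaque, numbered, used in sequence, logged or prepared by someone other than the person drawing them. No blocking is stated.

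The operating steps in section 6.1.5 have the technician or imager size and position the novel rest. Section 4.2.2 has the Imager time the acquisition. Section 10.3 tests one pooled preference proportion and names only inter-eye correlation in the time model. Neither analysis has an order term.

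**The concern.** When each subject tries both devices, the 50% null for preference is protected from session effects only if order is balanced and is not chosen to suit the subject. If people tend to prefer the first session (less fatigue) or the second (recency), putting the novel device more often in the favoured session moves the preference proportion away from 50% with no device effect. Acquisition time has the same exposure.

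Here the person who draws the order knows the device, fits it and measures the secondary endpoint. Drawing from an unnumbered pile leaves no record of whether the first envelope drawn was the one used. The analysis has nothing that would reveal or correct a resulting imbalance.

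The count conflict adds a route that needs no intent. If 90 envelopes are supplied and about 150 subjects enrol, someone must improvise an order for the last 60.

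**Working it through.** **Inputs from the documents.** Envelopes: 90 (6.1.5) or 150 (schematic). Subjects: about 150 (5.6) or 90 (2.3, 10.2). Order is split evenly over the whole pile (6.1.5). Two-sided exact test of 50% at 0.05 (10.2).

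**The plan's own figure.** For N=90, the exact two-sided cut-off is 55 of 90 (actual alpha 0.0446). Power at 65.7% is then 84.8%, not the stated 80%. The difference is on the safe side and does not affect this point. For N=150 the cut-off is 88 (actual alpha 0.041).

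**Assumed, because the documents give no figure.** With no device effect, a subject prefers the device in the favoured session with probability 0.5 + d. I use d = 0.1 (a 60:40 tilt) and show d = 0.2 and 0.3 as the range.

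**Formula.** If the novel device is in the favoured session for a share f of subjects, the expected preference for it is 0.5 + (2f − 1)d. The false-positive rate is the chance that the sum of two binomials, one per order group, passes the exact cut-off in either direction.

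**Largest imbalance when each envelope is used at most once and none is discarded**

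- 150 envelopes, 150 subjects: 75:75, so f = 0.50, whatever the drawing.
- 90 envelopes, 90 subjects: 45:45, so f = 0.50.
- 90 envelopes, 150 subjects: 150 − 90 = 60 subjects have no envelope. If all 60 get the same order, 45 + 60 = 105, giving 105:45 and f = 0.70.
- 150 envelopes, 90 subjects: up to 75:15, so f = 0.83, but only by deliberate selection.

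**Worst case for 90 envelopes and 150 subjects.** At d = 0.1, expected preference is 0.5 + (2 × 0.70 − 1) × 0.1 = 0.54.

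| N=150, no device effect | d = 0.1 | d = 0.2 | d = 0.3 |
|---|---|---|---|
| Balanced 75:75 | 3.7% | 2.6% | 1.1% |
| 105:45 | 14.0% | 46.6% | 86.9% |

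The excess favours the novel device if it is over-represented in the favoured session, and the conventional device if it is under-represented.

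**Leftover envelopes, honest draws.** For 90 draws from 150 (75 of each order), the count in one order is hypergeometric: 95% of draws give 39 to 51 of 90, and there is a 13% chance of 50:40 or worse. Averaged over such draws, the false-positive rate is 4.2%, 3.5% and 2.3% for d = 0.1, 0.2 and 0.3. For 140 draws from 150, the worst possible split is 75:65. At d = 0.1 it gives 3.3%.

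**Cells.** Neither count divides evenly over the four device-by-eye combinations (90/4 = 22.5; 150/4 = 37.5), although each factor alone can be split evenly.

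**The case against.** The strongest reply is that a mixed pile most naturally means a shuffled, blind draw. Envelopes imply some concealment, every subject gets both devices, and the documents describe no re-drawing. The favoured session is unknown, so it is not clear which way anyone would steer. All of that is fair, and nothing here suggests misconduct. What stands is that the method would neither prevent nor show a departure from a blind draw.

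A reader might infer two stronger things.

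- **That leftover envelopes bias the result by themselves.** They do not. Honest draws give chance imbalance, and the average error rate stays below 5%.
- **That splits such as 80:20 could arise at N=150.** The pile as described does not allow it. With 150 envelopes the split is 75:75, since an envelope put back must be used later, and with 90 envelopes it cannot pass 105:45.

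If the whole pile is used, the only remaining route is matching orders to types of subject. The documents give no basis for putting a size on that.

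On the remedy, small fixed blocks would be easier for unmasked staff to predict than a large pile. That objection is right, and block sizes should vary.

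**Conclusion.** The concern holds as a weakness in allocation control together with a count that must be reconciled. It does not show that the result will be biased. An unmasked Imager chooses order from an unnumbered pile with no audit trail, and the analysis has no order term.

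The one imbalance that can be sized from the documents' own counts is 105:45. It requires the 90-envelope figure to be the operative one and all 60 unassigned subjects to receive the same order. At a 60:40 session tilt it raises the false-positive rate from about 4% to about 14%. The tilt is an assumption, and a larger tilt gives a larger rate. With 150 envelopes fully used there is no total imbalance at all. The change is worth making before enrolment, because concealment cannot be restored afterwards.

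**What to change.** 1. Reconcile the envelope count in section 6.1.5 and the schematic with the enrolment target, so that every subject has a pre-assigned order.
2. Replace the mixed pile with sequentially numbered, opaque, sealed envelopes. The statistician prepares them in permuted blocks over the four combinations of device order and first eye. Vary the block size at random (for example 4 and 8) and do not disclose it to clinic staff.
3. Prepare whole blocks past the target: for 150 subjects, at least 38 × 4 = 152 envelopes. An incomplete last block then leaves a device-order difference of at most half its size (2 for a block of 4, 4 for a block of 8).
4. After consent and confirmed eligibility, the coordinator takes the next number, records subject ID and time before opening it, and logs it. Coordinators sit on the group that reviews cumulative data (section 8.1.1), so the safeguard is the numbering and the log rather than the person.
5. As a cheap addition in section 10.3, include an order-stratified sensitivity analysis of preference and an order term in the time model.

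**Cost.** Short edits to sections 6.1.5 and 10.3 and to the schematic, IRB approval of the amendment (section 12.2), and a little statistician and coordinator time.
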